## **XIII. Statistics**

Power analysis is done on the assumption that DGF will be reduced at least by 10% using MP vs. CS. For a power of 0.80 with  $p < 0.05$ , the expected sample size (N) is 300 donors with 300 donor kidneys in either MP or CS, respectively.

Statistical analysis of demographic donor and recipient characteristics will be carried out to check adequate randomization and find relevant differences. To account for the within-donor dependence structure of the data, a multivariate model will be built with a normal gamma frailty term for the donor.

A paired study design leads to a situation in which each donor is the perfect match to himself. On average both treatment arms will have an equal distribution of known and unknown prognostic factors. However, there is no assurance that all prognostic factors are evenly distributed. Therefore, an a posteriori stratification will be performed, implying a modeling of the data using the appropriate multivariate analysis technique. The following preservation and recipient factors are associated with early renal graft dysfunction and thus will be included in the stratification: preservation time (cold ischemic time = CIT), number of HLA mismatches, recent PRA level, recipient age, 1st/retransplant, length of time on dialysis, donor source (e.g. traditional, expanded, non-heart beating) and donor age. Correlation of perfusate organ function testing information to post-transplant graft function and survival will also be done. Lastly, a cost-benefit analysis of the two modalities as regards to graft outcome and survival will be performed.

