### Primary endpoint:

DGF, defined as any dialysis requirement within 7 days post transplant.

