## **XII. Epidemiology**

DGF is reported to be 25-35% after CS preservation. MP is expected to reduce this rate by 10% (RR 0.9). DGF rates for extended criteria donors and NHB kidney donors are higher, and results will be included in the overall analysis with the possibility of stratification.

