**XVI. Addendum 2: Recipient ID and Operation Parameters**

Recipient identification

Kidney received:  left kidney  right kidney  
ET donor number: |\_|\_|\_|\_|\_|\_|\_|\_|  
ET recipient number: |\_|\_|\_|\_|\_|\_|\_|\_|  
Name recipient transplantation center: \_\_\_\_\_  
Recipient date of birth (dd-mm-yy): \_\_-\_\_-\_\_  
Recipient sex:  male  female  
Renal disease: \_\_\_\_\_  
Number of previous transplants: \_\_\_\_\_  
Pre-transplant diuresis: \_\_\_\_\_ ml/24h  
Recipient blood group:  O  A  B  AB  
Recipient HLA-typing: A \_\_\_\_\_ B \_\_\_\_\_ DR \_\_\_\_\_  
ET-urgency:  0  1  2  4  
Number of HLA mismatches: A |\_|\_| B |\_|\_| DR |\_|\_|

Recipient operation – peri-operative data

Transplantation date (dd-mm-yy): \_\_-\_\_-\_\_  
Start time operation (induction of anesthesia) (hh:mm): \_\_\_\_:\_\_\_\_  
Mannitol:  yes  no  
Diuretics:  yes  no  
Dopamine:  yes  no  
Hypotensive period (syst. < 100 mmHg):  yes  no  
    lowest systolic blood pressure: \_\_\_\_\_ mmHg  
    lowest diastolic blood pressure: \_\_\_\_\_ mmHg  
    duration hypotensive period: \_\_\_\_\_ minutes  
CVP during anastomosis:  deceased  normal  increased  
Incision:  med. laparotomy  extraperitoneal  
Transplant side:  left  right  
Arterial problems:  
     no  
     ligated polar artery  
     reconstructed polar / hilar artery  
     repaired intima dissection  
     other  
Venous problems:  yes  no  
Start time anastomosis (hh:mm): \_\_\_\_:\_\_\_\_  
Total anastomosis time: \_\_\_\_\_ minutes  
Reclamping time: \_\_\_\_\_ minutes  
Time of reperfusion (hh:mm): \_\_\_\_:\_\_\_\_  
Cold ischemia period: \_\_\_\_\_ hours \_\_\_\_\_ minutes  
Remarks: \_\_\_\_\_

Recipient operation – perfusion characteristics

Upper pole:  smooth  spotted  infarction  
Middle pole:  smooth  spotted  infarction  
Lower pole:  smooth  spotted  infarction  
Intra-operative diuresis:  yes  no  unknown  
Remarks: \_\_\_\_\_

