**XVII. Addendum 3: Recipient Follow Up Parameters**

Kidney graft failure day 1 – 14

Graft failure:  yes  no

Date of graft failure (dd-mm-yy): \_\_-\_\_-\_\_

Primary cause:

- immunologic
- preservation
- technical - arterial
- technical – venous
- infection – bacterial
- infection – viral
- other

Graft removal:  yes  no

Death:  yes  no

Date of death (dd-mm-yy): \_\_-\_\_-\_\_

Cause of death:  Tx-related  non-Tx-related

Hypotensive periods first 24 hours post-transplant

Hypotensive period I:  yes  no

duration: \_\_\_\_\_ minutes

lowest systolic blood pressure: \_\_\_\_\_ mmHg

lowest diastolic blood pressue: \_\_\_\_\_ mmHg

Hypotensive period II:  yes  no

duration: \_\_\_\_\_ minutes

lowest systolic blood pressure: \_\_\_\_\_ mmHg

lowest diastolic blood pressue: \_\_\_\_\_ mmHg

Serum creatinine and creatinine clearance day 1 - 14

Serum creatinine day 1: \_\_\_\_\_ umol/l

Serum creatinine day 2: \_\_\_\_\_ umol/l

Serum creatinine day 3: \_\_\_\_\_ umol/l

Serum creatinine day 4: \_\_\_\_\_ umol/l

Serum creatinine day 5: \_\_\_\_\_ umol/l

Serum creatinine day 6: \_\_\_\_\_ umol/l

Serum creatinine day 7: \_\_\_\_\_ umol/l

Creatinine clearance day 7: \_\_\_\_\_ ml/min.

Serum creatinine day 8: \_\_\_\_\_ umol/l

Serum creatinine day 9: \_\_\_\_\_ umol/l

Serum creatinine day 10: \_\_\_\_\_ umol/l

Serum creatinine day 11: \_\_\_\_\_ umol/l

Serum creatinine day 12: \_\_\_\_\_ umol/l

Serum creatinine day 13: \_\_\_\_\_ umol/l

Serum creatinine day 14: \_\_\_\_\_ umol/l

Creatinine clearance day 14: \_\_\_\_\_ ml/min.

Fluid intake and diuresis day 1 - 14

Day 1 diuresis: \_\_\_\_\_ ml

Day 2 diuresis: \_\_\_\_\_ ml

Day 3 diuresis: \_\_\_\_\_ ml

Day 4 diuresis: \_\_\_\_\_ ml

Day 5 diuresis: \_\_\_\_\_ ml

Day 6 diuresis: \_\_\_\_\_ ml

Day 7 diuresis: \_\_\_\_\_ ml  
Day 8 diuresis: \_\_\_\_\_ ml  
Day 9 diuresis: \_\_\_\_\_ ml  
Day 10 diuresis: \_\_\_\_\_ ml  
Day 11 diuresis: \_\_\_\_\_ ml  
Day 12 diuresis: \_\_\_\_\_ ml  
Day 13 diuresis: \_\_\_\_\_ ml  
Day 14 diuresis: \_\_\_\_\_ ml

Immunosuppressive therapy and rejection

Prednisolon:  yes  no  
Cyclosporin:  yes  no  
Tacrolimus:  yes  no  
Azathioprine:  yes  no  
MMF:  yes  no  
ATG:  yes  no  
IL-2 receptor antagonists:  yes  no  
Other immunosuppressive drugs: \_\_\_\_\_  
Number of treatments for rejection day 1 - 14:  
    Prednisolon: \_\_\_\_\_  
    Other: \_\_\_\_\_  
Rejection biopsy proven:  yes  no  

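### The factors named for the adjusted DGF analysis omit recipient pre-transplant diuresis, a baseline field on the recipient form; adding it is a cheap improvement with a modest gain in power

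*Protocol*

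**What the plan says.** The primary endpoint (section III) is "DGF, defined as any dialysis requirement within 7 days post transplant".

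Section XIII plans a multivariate model with a donor frailty term. Because prognostic factors may still be unevenly distributed, it adds an a posteriori stratification, which it describes as modelling. It introduces the factors with "The following preservation and recipient factors are associated with early renal graft dysfunction and thus will be included in the stratification" and names cold ischaemic time, HLA mismatches, recent PRA, recipient age, first or repeat transplant, time on dialysis, donor source and donor age.

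The recipient form in Addendum 2 has the field "Pre-transplant diuresis", in ml per 24 hours. It is not among the eight factors. Urine output is recorded again after surgery under "Fluid intake and diuresis day 1 - 14" in Addendum 3.

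On size, section XII states "DGF is reported to be 25-35% after CS preservation", and section XIII states "Power analysis is done on the assumption that DGF will be reduced at least by 10% using MP vs. CS", with 300 donors for power 0.80 at p < 0.05.

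**The concern.** Donor pairing removes donor differences from the comparison but not recipient differences, since each pair has two recipients. A recipient who still passes urine may need less dialysis in the first week however the graft performs, so native output plausibly meets the protocol's own selection rule of association with early graft dysfunction. Donor age and donor source are the same for both kidneys of a pair and cannot correct a recipient imbalance; only factors that differ within the pair can.

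The variable is also safe to adjust for. It describes the recipient before transplantation, and section VII and Addendum 4 withhold the preservation method until the centre has made its choice or accepted the offer. Cold ischaemic time, which is on the list, accrues after randomisation, so diuresis is the cleaner baseline covariate.

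At stake are some power for the primary comparison and correction of any chance difference in native output between arms.

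**Working it through.** **Inputs.** From the documents: a binary endpoint, 25–35% DGF under cold storage, a 10% reduction, 300 donors with one kidney per arm, power 0.80, p < 0.05. Assumed: a two-sided test, and a standard-normal recipient covariate with an odds ratio (OR) for DGF per standard deviation (SD) of 1.3 to 3.0. The documents give no value for that OR.

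**1. The plan's own figure.** For 30% v 20%, two-sided 0.05 and power 0.80:

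n = [1.96·√(2·0.25·0.75) + 0.842·√(0.3·0.7 + 0.2·0.8)]² / 0.10² = 293.2, so 294 per arm; power at 300 is 0.809.

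This agrees with 300, but only if 10% means ten percentage points from the middle of the stated range. With the relative risk of 0.9 given in section XII, 30% v 27% needs 3,554 per arm, and power at 300 is 0.126. That conflict is a separate matter and more important than this one. The absolute reading is used below. The planned 300 is reproduced without any covariate, so this point does not change it.

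**2. Ordinary logistic model, independent kidneys.** 35% v 25%, 300 per arm, 3,000 simulated trials per row. Each cell shows the value without → with the covariate.

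| Assumed OR per SD | Treatment log OR | SE of log OR | Power | Change in variance of standardised risk difference |
|---|---|---|---|---|
| 1.3 | −0.479 → −0.487 | 0.181 → 0.182 | 0.761 → 0.767 | −2% |
| 1.6 | −0.485 → −0.507 | 0.181 → 0.185 | 0.763 → 0.779 | −3% |
| 2.0 | −0.483 → −0.530 | 0.181 → 0.190 | 0.765 → 0.791 | −8% |
| 2.5 | −0.484 → −0.562 | 0.181 → 0.195 | 0.771 → 0.840 | −16% |

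The SE of the log OR rises with adjustment. Power rises because the conditional log OR grows by more: at OR 2.0 the ratio of estimate to SE goes from 0.483/0.1805 = 2.68 to 0.530/0.1896 = 2.80. With an uninformative covariate (OR 1.0), power is unchanged within simulation error (0.768 and 0.764). Monte Carlo error of each power figure is about 0.8 points.

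**3. Paired design.** 300 pairs, 30% v 20%, assumed donor-effect SD 0.7, 6,000 trials per row. The within-pair difference in DGF was regressed on the within-pair difference in the covariate.

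| Assumed OR per SD | Power without → with | Change in variance of risk difference |
|---|---|---|
| 1.3 | 0.84 → 0.84 | −1% |
| 1.6 | 0.84 → 0.85 | −3% |
| 2.0 | 0.83 → 0.86 | −7% |
| 2.5 | 0.83 → 0.87 | −11% |
| 3.0 | 0.83 → 0.88 | −14% |

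A re-run with a different random seed agreed within about one power point.

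**4. Range.** Steps 2 and 3 together give about 0 to 3 points for OR 1.3 to 2.0 and about 4 to 7 points at 2.5. If the true effect were the relative risk of 0.9 (30% v 27%), the covariate would add at most about one point: 0.126 → 0.135 at OR 1.6 and 0.131 → 0.132 at OR 2.0.

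**5. Overlap with time on dialysis.** Illustration with assumed correlations: diuresis with DGF 0.30, dialysis time with DGF 0.25, the two with each other 0.50. Joint R² = (0.09 + 0.0625 − 2·0.30·0.25·0.50)/(1 − 0.25) = 0.103. Beyond dialysis time, diuresis removes (0.103 − 0.0625)/(1 − 0.0625) ≈ 4% of the remaining variance, against 9% on its own. The linear scale is used here only to show how overlap shrinks the gain.

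**The case against.** The strongest reply is that nothing here is an error. Section XIII says the named factors will be included, not that no others will be. It also plans a check for relevant donor and recipient differences, and a statistical analysis plan may add covariates. No passage says that urine output predicts dialysis or how strongly, so every gain shown rests on an assumption. Time on dialysis is already listed and may carry much of the same information.

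Most of this stands, and it limits the point to an improvement. It does not remove it: the protocol commits to a named list under a stated selection rule, and a factor added after outcomes are known would be post hoc. On overlap, the recipient form has no field for time on dialysis, although a registry may supply it, while diuresis does have a field.

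Three stronger readings are tempting, and the documents do not support them.

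- A reader might infer that the interval for the treatment effect is needlessly wide. On the log-odds scale of a logistic model the SE rises with adjustment, and the same should be expected of a frailty model. The benefit lies in power or in a standardised risk difference. The rule that variance falls by the squared correlation belongs to linear models.
- A reader might infer that the randomised comparison is biased or 300 donors too few. Leaving out a baseline covariate does neither.
- A reader might infer that the value exists for every recipient and costs nothing to use. A form field does not show completeness. In Scenario 3 of Addendum 4 no perfusionist attends, and recipient data are requested from the centre in the same way as for ice-stored kidneys. Completeness could therefore differ by region and perhaps by arm, and under complete-case handling one missing value can cost a whole pair.

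**Conclusion.** The point holds as a cheap improvement. A baseline recipient value that has its own field on the form, plausibly bears on a dialysis-based endpoint and differs within pairs is left out of the named factors. The loss is modest: about 0 to 3 power points at an assumed OR per SD of 1.3 to 2.0, and about 4 to 7 at 2.5. These are upper-end figures, because the simulations credit diuresis with information that time on dialysis may already hold. They also rest on an absolute ten-point effect, a normally distributed covariate, complete data, and logistic or within-pair linear models rather than the planned frailty model. Validity and the sample size are not affected.

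**What to change.** Before outcome data are seen, amend section XIII as follows.

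- Add recipient pre-transplant diuresis (ml/24h, Addendum 2) to the named factors, as a continuous term in the donor-paired model for DGF, for example log(ml + 1).
- State a missing-value rule that keeps pairs in the analysis, for example imputation blind to outcome with a missingness indicator. Tabulate missingness by arm first; an indicator is safe only if missingness does not depend on the arm. Obtaining the value by the same route for both recipients of a pair would help.
- Report the unadjusted paired comparison beside the adjusted one.

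The cost is one extra term and no new form field. The real work is following up and handling missing values, above all from centres outside the trial region.

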**XIV. Study Schedule**

Phase I – Pre-Study Preparation

	Estimated Time to Completion	Responsible Party
"All Hands" organizational meeting including PI's, RPC supervisors, key ORS, ET personnel. Purpose: 
 
1. Introduce participants, define roles & responsibilities and trial branding
 
2. Provide study overview, outcomes
 
3. Define common outcomes terminology e.g. long and short term graft survival, graft function
 
4. Define scope, frequency and authorship of study reports
 
5. Establish RPC site development for The Netherlands, Belgium and Nordrhein Westfalen and training schedule NRW and The Netherlands
 
	Within first 30 days of signing the definitive study sponsorship	ORS will host at its Zaventem (Brussels) facility
Forms/documentation development	Within first 60 days of study agreement signing	PI's & CTA
Further information of key persons (e.g. donor & tx surgeons, TC's, tx nephrologists) in respective regions for collaboration and relevant agreements signed by participant hospitals as necessary		PI's & CTA
Database development		PI's & CTA

Phase II – Transplantation

	Estimated Time to Completion	Responsible Party
Paired kidney procurement, preservation (static/perfusion), & transplantation	10-12 months	Participant hospitals & RPC's
Interim reports issued (Content to be determined in initial organizational meeting as described above)	Quarterly	PI's & CTA hosted by ORS

Phase III – Data Analysis and Final Report

	Estimated Time to Completion	Responsible Party
Final data analysis and draft final report generation	Within 14 months of last Study transplant procedure	PI's & stat
PI final meeting		PI's & CTA
Final report submission		PI's & CTA

CTA = Central Trial Assistance - Eurotransplant  
 ORS = Organ Recovery Systems  
 PI = Principal Investigator  
 RPC = Regional Perfusion Center

**XV. Addendum 1: Donor Parameters**

Donor identification

ET Donor number: |\_|\_|\_|\_|\_|\_|\_|\_|  
Name donor center: \_\_\_\_\_  
Date of admission (dd-mm-yy): \_\_-\_\_-\_\_  
Date of donor operation (dd-mm-yy): \_\_-\_\_-\_\_  
Kidney left donated:  yes  no  
Kidney right donated:  yes  no  
Liver donated:  yes  no  
Lung donated:  yes  no  
Heart donated:  yes  no  
Pancreas donated:  yes  no  
Other organ donated: \_\_\_\_\_  
Donor date of birth (dd-mm-yy): \_\_-\_\_-\_\_  
Donor sex:  male  female  
Donor weight: \_\_\_\_\_ kg  
Donor blood group:  O  A  B  AB  
HLA-typing: A \_\_\_\_\_ B \_\_\_\_\_ DR \_\_\_\_\_

Donor pre-operative clinical data

Diagnosis:  
 multi trauma  
 trauma capitis  
 intra cranial bleeding  
 primary brain tumor  
 cardiomyopathy  
 other

Diabetes Mellitus (IDDM):  yes  no  
DM family history:  yes  no  
Alcohol abuse:  yes  no  
Cardiac arrest  yes  no  
Systolic blood pressure (mean): \_\_\_\_\_ mmHg  
Diastolic blood pressure (mean): \_\_\_\_\_ mmHg  
Hypotensive period (syst. < 100 mmHg):  yes  no  
    number of hypotensive periods: \_\_\_\_\_  
    lowest systolic blood pressure: \_\_\_\_\_ mmHg  
    lowest diastolic blood pressure: \_\_\_\_\_ mmHg  
    duration lowest hypot. period: \_\_\_\_\_ minutes  
Mean diuresis / hr. last 24 hrs.: \_\_\_\_\_ ml  
Donor anuria / oliguria (< 500 ml/24h):  yes  no  
    duration an-/oliguria: \_\_\_\_\_ hours

Vasopressors:  
Dopamine:  yes  no | Last dose: \_\_\_\_\_ mg  
Dobutamine:  yes  no | Last dose: \_\_\_\_\_ mg  
(Nor)adrenaline:  yes  no | Last dose: \_\_\_\_\_ mg  
Others: \_\_\_\_\_ | Last dose: \_\_\_\_\_ mg

Other relevant data: \_\_\_\_\_

Donor operation data

Donor heart beating:  yes  no  
If NHBD:

Maastricht category:  1  2  3  4  
Time of detubation (hh:mm): \_\_\_\_:\_\_\_\_  
Time of cardiac arrest (hh:mm): \_\_\_\_:\_\_\_\_  
Time of start perfusion (hh:mm): \_\_\_\_:\_\_\_\_  
Hypotensive period (syst. < 100 mmHg):  yes  no  
lowest systolic blood pressure: \_\_\_\_ mmHg  
lowest diastolic blood pressure: \_\_\_\_ mmHg  
duration hypotensive period: \_\_\_\_ minutes  
Donor anuria / oliguria:  yes  no  
Diuresis last hour: \_\_\_\_\_ ml  
Phenoxybenzamin (Dibenzylin):  yes  no  
Fentolamine (Regitin):  yes  no  
Prostaglandins:  yes  no  
Others: \_\_\_\_\_  
Heparin:  yes  no

**Donor operation left kidney**

Preservation modality:  CS  MP  
Preservation solution (if CS):  UW  HTK  
Number of renal arteries left: \_\_\_\_\_  
Arterial damage:  yes  no  
Venous damage:  yes  no  
Ureteral damage:  yes  no  
Parenchymal damage:  yes  no  
Washout perfusion left kidney:  homogenous  patchy  blue  
Washout parameters:  
Volume of washout with UW/HTK: \_\_\_\_\_ ml  
Cross clamping time + start washout (hh:mm): \_\_\_\_:\_\_\_\_  
Removal time left kidney (hh:mm): \_\_\_\_:\_\_\_\_  
Visible perfusion defects:  yes  no  
Warm ischemia period: \_\_\_\_ minutes  
Time points transport:  
Leaving donor hospital (hh:mm): \_\_\_\_:\_\_\_\_  
Arrival at holding (if applicable) (hh:mm): \_\_\_\_:\_\_\_\_  
Departure of holding (if applicable) (hh:mm): \_\_\_\_:\_\_\_\_  
Arrival at recipient hospital (hh:mm): \_\_\_\_:\_\_\_\_  
Name recipient transplantation center: \_\_\_\_\_  
Number of recipient: \_\_\_\_\_

**Donor operation right kidney**

Preservation modality:  CS  MP  
Preservation solution (if CS):  UW  HTK  
Number of renal arteries right: \_\_\_\_\_  
Arterial damage:  yes  no  
Venous damage:  yes  no  
Ureteral damage:  yes  no  
Parenchymal damage:  yes  no  
Washout perfusion right kidney:  homogenous  patchy  blue  
Washout parameters:  
Volume of washout with UW/HTK: \_\_\_\_\_ ml  
Cross clamping time + start washout (hh:mm): \_\_\_\_:\_\_\_\_  
Removal time right kidney (hh:mm): \_\_\_\_:\_\_\_\_  
Visible perfusion defects:  yes  no  
Warm ischemia period: \_\_\_\_ minutes

Time points transport:

Leaving donor hospital (hh:mm): \_\_\_\_:\_\_\_\_

Arrival at holding (if applicable) (hh:mm): \_\_\_\_:\_\_\_\_

Departure of holding (if applicable) (hh:mm): \_\_\_\_:\_\_\_\_

Arrival at recipient hospital (hh:mm): \_\_\_\_:\_\_\_\_

Name recipient transplantation center: \_\_\_\_\_

Number of recipient: \_\_\_\_\_

Donor laboratory values (last available values)

Hb: \_\_\_\_\_ mmol/l

Ht: \_\_\_\_\_

pH: \_\_\_\_\_

pCO2: \_\_\_\_\_ Pa

pO2: \_\_\_\_\_ Pa

Urea: \_\_\_\_\_ mmol/l

Mean creatinine: \_\_\_\_\_ umol/l

Max. creatinine: \_\_\_\_\_ umol/l

**XVI. Addendum 2: Recipient ID and Operation Parameters**

Recipient identification

Kidney received:  left kidney  right kidney  
ET donor number: |\_|\_|\_|\_|\_|\_|\_|\_|  
ET recipient number: |\_|\_|\_|\_|\_|\_|\_|\_|  
Name recipient transplantation center: \_\_\_\_\_  
Recipient date of birth (dd-mm-yy): \_\_-\_\_-\_\_  
Recipient sex:  male  female  
Renal disease: \_\_\_\_\_  
Number of previous transplants: \_\_\_\_\_  
Pre-transplant diuresis: \_\_\_\_\_ ml/24h  
Recipient blood group:  O  A  B  AB  
Recipient HLA-typing: A \_\_\_\_\_ B \_\_\_\_\_ DR \_\_\_\_\_  
ET-urgency:  0  1  2  4  
Number of HLA mismatches: A |\_|\_| B |\_|\_| DR |\_|\_|

Recipient operation – peri-operative data

Transplantation date (dd-mm-yy): \_\_-\_\_-\_\_  
Start time operation (induction of anesthesia) (hh:mm): \_\_\_\_:\_\_\_\_  
Mannitol:  yes  no  
Diuretics:  yes  no  
Dopamine:  yes  no  
Hypotensive period (syst. < 100 mmHg):  yes  no  
    lowest systolic blood pressure: \_\_\_\_\_ mmHg  
    lowest diastolic blood pressure: \_\_\_\_\_ mmHg  
    duration hypotensive period: \_\_\_\_\_ minutes  
CVP during anastomosis:  deceased  normal  increased  
Incision:  med. laparotomy  extraperitoneal  
Transplant side:  left  right  
Arterial problems:  
     no  
     ligated polar artery  
     reconstructed polar / hilar artery  
     repaired intima dissection  
     other  
Venous problems:  yes  no  
Start time anastomosis (hh:mm): \_\_\_\_:\_\_\_\_  
Total anastomosis time: \_\_\_\_\_ minutes  
Reclamping time: \_\_\_\_\_ minutes  
Time of reperfusion (hh:mm): \_\_\_\_:\_\_\_\_  
Cold ischemia period: \_\_\_\_\_ hours \_\_\_\_\_ minutes  
Remarks: \_\_\_\_\_

Recipient operation – perfusion characteristics

Upper pole:  smooth  spotted  infarction  
Middle pole:  smooth  spotted  infarction  
Lower pole:  smooth  spotted  infarction  
Intra-operative diuresis:  yes  no  unknown  
Remarks: \_\_\_\_\_

**XVII. Addendum 3: Recipient Follow Up Parameters**

Kidney graft failure day 1 – 14

Graft failure:  yes  no

Date of graft failure (dd-mm-yy): \_\_-\_\_-\_\_

Primary cause:

- immunologic
- preservation
- technical - arterial
- technical – venous
- infection – bacterial
- infection – viral
- other

Graft removal:  yes  no

Death:  yes  no

Date of death (dd-mm-yy): \_\_-\_\_-\_\_

Cause of death:  Tx-related  non-Tx-related

Hypotensive periods first 24 hours post-transplant

Hypotensive period I:  yes  no

duration: \_\_\_\_\_ minutes

lowest systolic blood pressure: \_\_\_\_\_ mmHg

lowest diastolic blood pressue: \_\_\_\_\_ mmHg

Hypotensive period II:  yes  no

duration: \_\_\_\_\_ minutes

lowest systolic blood pressure: \_\_\_\_\_ mmHg

lowest diastolic blood pressue: \_\_\_\_\_ mmHg

Serum creatinine and creatinine clearance day 1 - 14

Serum creatinine day 1: \_\_\_\_\_ umol/l

Serum creatinine day 2: \_\_\_\_\_ umol/l

Serum creatinine day 3: \_\_\_\_\_ umol/l

Serum creatinine day 4: \_\_\_\_\_ umol/l

Serum creatinine day 5: \_\_\_\_\_ umol/l

Serum creatinine day 6: \_\_\_\_\_ umol/l

Serum creatinine day 7: \_\_\_\_\_ umol/l

Creatinine clearance day 7: \_\_\_\_\_ ml/min.

Serum creatinine day 8: \_\_\_\_\_ umol/l

Serum creatinine day 9: \_\_\_\_\_ umol/l

Serum creatinine day 10: \_\_\_\_\_ umol/l

Serum creatinine day 11: \_\_\_\_\_ umol/l

Serum creatinine day 12: \_\_\_\_\_ umol/l

Serum creatinine day 13: \_\_\_\_\_ umol/l

Serum creatinine day 14: \_\_\_\_\_ umol/l

Creatinine clearance day 14: \_\_\_\_\_ ml/min.

Fluid intake and diuresis day 1 - 14

Day 1 diuresis: \_\_\_\_\_ ml

Day 2 diuresis: \_\_\_\_\_ ml

Day 3 diuresis: \_\_\_\_\_ ml

Day 4 diuresis: \_\_\_\_\_ ml

Day 5 diuresis: \_\_\_\_\_ ml

Day 6 diuresis: \_\_\_\_\_ ml

Day 7 diuresis: \_\_\_\_\_ ml  
Day 8 diuresis: \_\_\_\_\_ ml  
Day 9 diuresis: \_\_\_\_\_ ml  
Day 10 diuresis: \_\_\_\_\_ ml  
Day 11 diuresis: \_\_\_\_\_ ml  
Day 12 diuresis: \_\_\_\_\_ ml  
Day 13 diuresis: \_\_\_\_\_ ml  
Day 14 diuresis: \_\_\_\_\_ ml

Immunosuppressive therapy and rejection

Prednisolon:  yes  no  
Cyclosporin:  yes  no  
Tacrolimus:  yes  no  
Azathioprine:  yes  no  
MMF:  yes  no  
ATG:  yes  no  
IL-2 receptor antagonists:  yes  no  
Other immunosuppressive drugs: \_\_\_\_\_  
Number of treatments for rejection day 1 - 14:  
    Prednisolon: \_\_\_\_\_  
    Other: \_\_\_\_\_  
Rejection biopsy proven:  yes  no  
Calcineurin inhibitor toxicity day 1 - 14 (based on levels):  yes  no  
Remarks: \_\_\_\_\_

Dopamine and Lasix

Post-operative dopamine:  yes  no  
Post-operative Lasix:  yes  no

Dialysis requirement day 1 - 14

Dialysis type:  CAPD  hemodialysis  
Day 1 dialysis required:  yes  no  
Day 2 dialysis required:  yes  no  
Day 3 dialysis required:  yes  no  
Day 4 dialysis required:  yes  no  
Day 5 dialysis required:  yes  no  
Day 6 dialysis required:  yes  no  
Day 7 dialysis required:  yes  no  
Day 8 dialysis required:  yes  no  
Day 9 dialysis required:  yes  no  
Day 10 dialysis required:  yes  no  
Day 11 dialysis required:  yes  no  
Day 12 dialysis required:  yes  no  
Day 13 dialysis required:  yes  no  
Day 14 dialysis required:  yes  no

Discharge / readmission

Date of primary post-Tx discharge (dd-mm-yy): \_\_\_-\_\_\_-\_\_\_  
Readmission within 3 months post-tx:  yes  no  
    Reason for readmission: \_\_\_\_\_  
    Nr. of in hospital days after readmission: \_\_\_\_\_

Follow up at 1 month post transplantGraft failure:  yes  no

Date of graft failure (dd-mm-yy): \_\_\_-\_\_\_-\_\_\_

Primary cause:

 immunologic preservation technical - arterial technical - venous infection - bacterial infection - viral otherGraft removal:  yes  noDeath:  yes  no

Date of death (dd-mm-yy): \_\_\_-\_\_\_-\_\_\_

Cause of death:  Tx-related  non-Tx-related

Serum creatinine at 1 month: \_\_\_\_\_ umol/l

Creatinine clearance at 1 month: \_\_\_\_\_ ml/min.

Total nr. of dialysis treatments post-Tx: \_\_\_\_\_

Currently on dialysis:  yes  nodialysis type:  CAPD  hemodialysis

Date of last dialysis (dd-mm-yy): \_\_\_-\_\_\_-\_\_\_

Nr. of rejection periods (day 15 - 1 month): \_\_\_\_\_

Complications interfering with graft function not mentioned above: \_\_\_\_\_

Follow up at 3 months post transplantGraft failure:  yes  no

Date of graft failure (dd-mm-yy): \_\_\_-\_\_\_-\_\_\_

Primary cause:

 immunologic preservation technical - arterial technical - venous infection - bacterial infection - viral otherGraft removal:  yes  noDeath:  yes  no

Date of death (dd-mm-yy): \_\_\_-\_\_\_-\_\_\_

Cause of death:  Tx-related  non-Tx-related

Serum creatinine at 3 months: \_\_\_\_\_ umol/l

Creatinine clearance at 3 months: \_\_\_\_\_ ml/min.

Total nr. of dialysis treatments post-Tx: \_\_\_\_\_

Currently on dialysis:  yes  nodialysis type:  CAPD  hemodialysis

Date of last dialysis (dd-mm-yy): \_\_\_-\_\_\_-\_\_\_

Nr. of rejection periods (1 - 3 months): \_\_\_\_\_

Complications interfering with graft function not mentioned above: \_\_\_\_\_

Follow up at 1 year post transplantGraft failure:  yes  no

Date of graft failure (dd-mm-yy): \_\_\_-\_\_\_-\_\_\_

Primary cause:

 immunologic preservation

technical - arterial  
 technical - venous  
 infection - bacterial  
 infection - viral  
 other

Graft removal:  yes  no  
Death:  yes  no  
Date of death (dd-mm-yy): \_\_\_-\_\_\_-\_\_\_  
Cause of death:  Tx-related  non-Tx-related  
Serum creatinine at 1 year: \_\_\_\_\_ umol/l  
Creatinine clearance at 1 year: \_\_\_\_\_ ml/min.  
Total nr. of dialysis treatments post-Tx: \_\_\_\_\_  
Currently on dialysis:  yes  no  
    dialysis type:  CAPD  hemodialysis  
Date of last dialysis (dd-mm-yy): \_\_\_-\_\_\_-\_\_\_  
Nr. of rejection periods (3 - 12 months): \_\_\_\_\_  
Complications interfering with graft function not mentioned above: \_\_\_\_\_

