### Secondary endpoints:

Duration of DGF, renal function (serum creatinine; 1/creatinine; creatinine clearance; decrease of serum creatinine > 10% per day for at least 3 consecutive days for more than one week after tx; length of hospital stay; acute graft rejection, hyperkalemia, calcineurin inhibitor toxicity), graft and patient survival at 1-year.

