## **VIII. Data Collection**

### Donor, preservation and recipient data

Pertinent data (see addendum 1-3) for the study will be registered in a specially designed web-based database by the perfusionist during the donor, preservation and transplant procedure. Follow-up data (day 0-14, 1, 3 and 12 months) will be filed in the same secure online database by a member of the recipient team in the recipient center. Normal documentation for ET purposes will be carried out in the standard fashion. Recipient centers will be financially compensated for providing follow-up data to be used for the analysis of the study. ET ([name]) in close collaboration with the coordinating principal investigator ([name]) will monitor accrual and quality of data throughout the study. However all PI's share responsibility in encouraging data submission from their transplantation centers.

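### Recipient creatinine is listed only from day 1, although the data-collection text says follow-up starts at day 0: the first daily fall is lost and early creatinine cannot be adjusted for a pre-transplant value

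*Protocol*

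**What the plan says.** Section III lists the renal function measures among the secondary endpoints: serum creatinine, its reciprocal, creatinine clearance, and a rate-of-fall measure, "decrease of serum creatinine > 10% per day for at least 3 consecutive days". The sentence on that last measure then adds a qualifier about more than one week after transplantation, and its meaning is not clear.

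Section VIII makes the addenda the list of what is captured: "Pertinent data (see addendum 1-3) for the study will be registered in a specially designed web-based database". It gives the follow-up window as "Follow-up data (day 0-14, 1, 3 and 12 months) will be filed in the same secure online database".

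The addenda themselves contain:

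- **Addendum 3 (recipient follow-up):** a block headed "Serum creatinine and creatinine clearance day 1 - 14", whose first entry is "Serum creatinine day 1". Creatinine clearance is entered on days 7 and 14. Both are entered again at 1 month, 3 months and 1 year.
- **Addendum 2 (recipient and operation):** "Pre-transplant diuresis" is the only pre-transplant measure of the recipient's renal function. There is no creatinine.
- **Addendum 1 (donor):** creatinine appears under "Donor laboratory values (last available values", so it is the donor's.

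**The concern.** The body text and the form disagree on whether day 0 is captured. For recipient creatinine the form decides, because it lists the fields. Two things follow.

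First, the fall from the pre-transplant value to day 1 cannot be computed for any recipient. In a graft that works at once this is likely to be the steepest fall, so a rule that counts consecutive daily falls would judge such grafts on what is left after it.

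Second, the trial pairs by donor. The two recipients of a pair are different people with different creatinine values before surgery, and donor pairing does not remove that difference. A baseline covariate could remove part of it in the first days, but only if the value is recorded. A later analysis plan cannot adjust for, or count a fall from, a value that has no field.

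**Working it through.** The plan gives no figure to reproduce here. The check is a count, followed by an assumed model for size.

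**1. Count of usable changes.** With first value on day *f* and last on day *l*, daily changes = *l* − *f*, and windows of three consecutive changes = (*l* − *f*) − 2.

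| First value | Through day | Changes | Three-day windows |
|---|---|---|---|
| Day 0 (Section VIII) | 7 | 7 − 0 = 7 | 5 |
| Day 1 (Addendum 3) | 7 | 7 − 1 = 6 | 4 |
| Day 0 (Section VIII) | 14 | 14 − 0 = 14 | 12 |
| Day 1 (Addendum 3) | 14 | 14 − 1 = 13 | 11 |

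The loss is one change and one window per recipient. The earliest day on which a three-day run can be confirmed moves from day 3 to day 4. A recipient is classified differently only if the sole qualifying run is day 0 to day 3; a longer or later run is still found. Day 0 is taken here as the day of transplantation, before reperfusion; the protocol does not define it.

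**2. Who is affected (assumed curve).** Let C(t) = P + (C0 − P)·exp(−kt). Take C0 = 800 and P = 140 umol/l with a half-life of 0.6 day:

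- C(1) = 140 + 660 × 0.315 = 348
- C(2) = 140 + 660 × 0.0992 = 205
- C(3) = 140 + 660 × 0.0313 = 161
- C(4) = 140 + 660 × 0.0098 = 146

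The daily falls are 56.5%, 40.9%, 21.8% and 8.8%. With day 0 there are three consecutive falls above 10%; from day 1 there are only two. With starts of 500 or 800 and plateaus of 100-160 umol/l, the affected half-lives are 0.36-0.94 day, that is, fast recoverers.

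**3. How many (same curve, simulated).** There were 400,000 recipients per setting. C0 was normal with mean 750 and SD 150 or 250 (clipped to 300-1400), P lognormal with median 140 and log-SD 0.3, and k lognormal with median 0.25, 0.5 or 0.9 per day and log-SD 0.8. The share meeting the criterion only when day 0 is available was:

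- SD 150: 6.3%, 14.1%, 22.2%
- SD 250: 7.2%, 14.8%, 22.1%

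The loss can also shrink a contrast between arms. At SD 150, raising the median k from 0.25 to 0.5 raises the share meeting the criterion from 73.4% to 86.1% with day 0 (+12.7 points), but from 67.1% to 72.0% on the form as listed (+4.9 points).

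**4. Precision of the level comparisons (same model).** Variance removed by adjustment = r², where r is the correlation of C(t) with C0. The interval is shortened by 1 − √(1 − r²).

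| Day | r | Variance removed | Interval shorter by |
|---|---|---|---|
| 1 | 0.38-0.85 | 14-72% | 7-47% |
| 3 | 0.19-0.58 | 4-34% | 2-19% |
| 7 | 0.08-0.37 | 1-14% | 0.5-7% |

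For 1/creatinine the variance removed is smaller: about 1-18% on day 3 and 0-7% on day 7. By day 14 the gain is negligible on both scales.

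**The case against.** A reader might infer that, without a baseline, the creatinine endpoints as a whole are unusable or biased. The protocol does not support that. Serum creatinine, 1/creatinine and clearance are listed as levels, not as change from baseline. Both arms are measured on the same days. Preservation method is randomised within the donor, and centres choose left or right before the method is revealed (Section VII), so starting creatinine should balance on average. Its absence costs precision and does not bias the comparison. The primary endpoint is dialysis within 7 days and uses no creatinine. All of this stands.

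A reader might also take the 6-22% as a property of this trial. It is not. The documents give no creatinine level, spread or recovery rate, and the curve assumes that every graft recovers from time zero without dialysis, although Section XII gives delayed graft function of 25-35% after cold storage. Delaying onset by 1-8 days in 30% of grafts gives 4-16%, a half-day lag in all grafts gives 2-22%, and a log-SD of 0.4 gives 4-31%. If the more-than-one-week qualifier means that the measure is assessed only after week 1, the day 0 to day 1 fall is irrelevant and this part of the loss is zero.

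Three further points have some weight. The adjustment factors in Section XIII do not include pre-transplant creatinine, so adjusting for it is an improvement and not a correction of a stated analysis. The day 0 in Section VIII may describe follow-up data in general and not creatinine. Section XIV schedules forms and database development for Phase I, so the addenda may not be the final forms. Even so, Section VIII points to these addenda as the data to be registered, and the field is in none of them.

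**Conclusion.** The concern holds in limited form. The listed forms contain no recipient creatinine before day 1, although Section VIII starts follow-up at day 0. The certain cost is one daily change and one three-day window per recipient (1 of 7 and 1 of 5 in week 1) for the single change-based creatinine measure, provided that early falls count under its wording. The second cost is precision: early creatinine levels cannot be baseline-adjusted, which matters mainly on days 1-3 and little by day 7. The share of recipients reclassified and the variance removed rest wholly on the assumed recovery model. The level comparisons and the primary endpoint stay valid and unbiased. Importance is low to moderate and confined to secondary endpoints. The case for acting is that the remedy is cheap and an uncollected value is hard to recover uniformly later.

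**What to change.** - Add one field, *last serum creatinine before transplantation (umol/l)*, beside pre-transplant diuresis in Addendum 2 or as day 0 in Addendum 3, with the date of the last pre-transplant dialysis so that the value can be interpreted.
- State that first-week serum creatinine and 1/creatinine are compared with this value as a baseline covariate, and that daily falls are counted from it.
- Define day 0, and align the window in Section VIII with the fields in Addendum 3. If no field is added, correct Section VIII and state that the daily-fall measure starts with the change from day 1 to day 2.
- Clarify whether falls in the first week count under the rate-of-fall measure.

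The cost is one or two database fields, filled from a laboratory value and a dialysis record assumed to exist before surgery, with no extra procedure or patients. The drawbacks are some missing values, values influenced by the timing of dialysis, and negligible gain at day 14 and later.
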